## Registration of adverse events

At all trial visits, patients are checked for adverse events to the investigational medicinal product. All visits include measuring distant BCVA, IOP, pupil size and accommodation. The patients and parents will also be asked for subjective complaints and symptoms related to the investigational medicinal product. The number of trial visits is illustrated in Figure 2. Patient and parents will be instructed to contact the investigators immediately if vision gets worse, the eye or eye surroundings turns red and/or painful or they become sensitive to light, or experience halos around light sources. If the patient experiences an adverse event or reaction within the trial period, the patient will be monitored and/or treated for as long as it is relevant given the circumstances. Principle investigators will make the decision.

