respectively, in the 0.01% and 0.1% group. (32) Accommodation amplitude in the 0.01% group was reduced to only 11.3 diopters (from 16.2 diopters) compared with a reduction to 3.8 diopters (from 16.7 diopters) in the 0.1% group. The mean reduction in accommodation amplitude over 2 years treatment was 4.6 diopters and 10.1 diopters in the atropine 0.01% and 0.1% group, respectively. (32) In functional terms, the changes in accommodation meant that near visual acuity was not significantly impaired in the 0.01% group, whereas deficiencies were noted in the 0.1% group. (32) Mean distant best-corrected visual acuity (BCVA) was not affected by low-dose atropine, although 13% in both groups reported mild distance blur. (32) Regarding adverse reactions attributable to atropine, allergic reactions were most frequent in the ATOM 2 study with 3.2% experiencing allergic conjunctivitis and 0.8% experiencing an allergy-associated dermatitis, all of which were in the 0.1% group. From a total of 400 children, 6 children had other eye symptoms, 5 of which could be attributed to atropine treatment, including 1 case of ocular irritation and 1 case of blur in the atropine 0.01% group, and 2 cases of ocular irritation and 1 case of intolerable glare in the atropine 0.5% group. All reported side effects were reversible on stopping medication. No adverse events were deemed to be related to the use of atropine at any concentration. (32)

Patients who experience adverse effects during the study will provide data for the study to determine the rate of complications. Since the sample size calculation was made to account for dropout, additional inclusion of participants to replace excluded participants is not intended.

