#### Adverse events and reactions

Adverse event (AE): Any untoward event regarding a participant in the clinical trial treated with an investigational medicinal product, not necessarily linked to the treatment.

Adverse reaction (AR): Any harmful and untoward reaction to an investigational medicinal product with no regards to the dose.

Unexpected adverse reaction (UAR): An adverse reaction of which the character or severity does not match the description of adverse reactions in the summary product characteristics for the given investigational medicinal product.

Serious adverse event (SAE) or serious adverse reaction (SAR): An adverse event or reaction that, regardless of dose, results in death, is life-threatening, causes hospitalization, results in significant or sustained incapacity, or leads to a congenital anomaly or malformation.

Suspected unexpected serious adverse reaction (SUSAR): A suspected unexpected serious adverse reaction which was not expected.

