#### Reporting adverse effects to the authorities

As a rule, all adverse events will be registered in a clinical trial on medicinal drugs. However, due to the age, level of activity and healthy nature of the patients involved as well as the duration and logistic possibilities of the study considered, the sponsor-investigator request to waive from this requirement.

Therefore, adverse events and reactions that are considered normal reactions to an eye examination (including stinging when applying eye drops for the examinations and short-term photophobia and blurred vision following eye examination) will not be considered an AE/AR. The sponsor-investigator request that only the following organ-specific symptoms or any likely related symptoms will be reported during the study as AE/AR: visual symptoms (e.g. photophobia, blurred vision and difficulties reading and focusing on text on short distance); eye-related symptoms (e.g. red eye, dry eye, itching eye, stinging or painful eye, changes in lacrimation, allergic reactions such as papillary conjunctivitis, contact dermatitis and lid edema); symptoms of the eye surroundings (e.g. skin changes (i.e. itching, stinging, swelling, redness and dryness); systemic anticholinergic effects (e.g. dryness of skin, mouth and throat from decreased secretion from mucus membranes, flushing, gastrointestinal symptoms, urinary retention and tachycardia). At baseline, patients and parents will be asked to report if the patient has any known tendency within the listed symptoms, e.g. constipation, urinary problems or skin-related problems such as dry or eczematoid skin. For example, if a patient is reported to have a tendency to constipation at baseline, the registration and reporting of AE/AE during study participation will be based upon changes in existing symptoms at baseline.

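### The visit-level symptom question is worded by relation to the trial drug, which does not match the plan's own adverse-event definition or its cause-free symptom list

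*Combined protocol and SAP*

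**What the plan says.** Four parts of the combined protocol and SAP bear on how symptoms are collected.

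- **Visit question** (Registration of adverse events). The section opens with "At all trial visits, patients are checked for adverse events to the investigational medicinal product" and then adds "The patients and parents will also be asked for subjective complaints and symptoms related to the investigational medicinal product". It also has distance acuity, intraocular pressure, pupil size and accommodation measured at all visits. Families are told to make contact at once for worse vision, redness or pain in or around the eye, light sensitivity, or halos. Those contact instructions do not mention cause.
- **Definition** (Adverse events and reactions). An adverse event is "Any untoward event regarding a participant in the clinical trial treated with an investigational medicinal product, not necessarily linked to the treatment".
- **Reporting rule** (Reporting adverse effects to the authorities). The sponsor-investigator asks that "only the following organ-specific symptoms or any likely related symptoms will be reported during the study as AE/AR". The list covers visual symptoms, eye symptoms, symptoms of the surrounding skin, and systemic anticholinergic effects.
- **Baseline and change** (same section). "At baseline, patients and parents will be asked to report if the patient has any known tendency within the listed symptoms". For a child with such a tendency, later registration "will be based upon changes in existing symptoms at baseline".

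Adverse effects and reactions are a secondary endpoint. The Hypothesis section has one main hypothesis on the safety of 0.01% atropine and one on the safety of 0.1%.

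**The concern.** Both visit-level sentences are framed by relation to the drug, while the definition and the symptom list are not. A reporting rule can act only on symptoms that reach the investigator. If staff put the question as written, a family that does not connect an itchy eye or a dry mouth with the drops has no prompt to mention it.

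Two things are at stake. First, the absolute side-effect rates, on which the safety hypotheses rest, may be too low in every arm. That leans towards a conclusion of good tolerability. Second, the comparison with placebo may be biased if families' beliefs about their arm differ between arms. The section on risks cites pupil increases of about 1 mm on 0.01% and 3 mm on 0.1%, and accommodation falling to 3.8 diopters on 0.1%. Partial unmasking is therefore plausible, above all in the 0.1% loading phase.

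**Working it through.** **Step 1. Which listed symptoms depend on the visit question?** The plan gives no figure here, so this step compares the text.

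| Listed symptom group | Objective measure at all visits | Contact instruction without attribution |
|---|---|---|
| Blurred vision | distance acuity | worse vision |
| Near-focus difficulty | accommodation | partly, as worse vision |
| Photophobia | pupil size (indirect) | light sensitivity, halos |
| Red or painful eye | none | yes |
| Itching, dry eye, changed lacrimation | none | none |
| Itching or dryness of the skin around the eyes | none | none |
| Dry skin, mouth or throat; flushing; gastrointestinal symptoms; urinary retention; tachycardia | none | none |

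The last three rows rest mainly on what families are asked at visits. The concern applies there.

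**Step 2. How large could the effect be?** The documents give neither the share of families who believe they are on atropine nor the share who would report an unattributed symptom. Both are assumed.

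- *t*: true symptom rate, equal in both arms. The value 13% is the plan's cited rate of mild distance blur in two atropine groups. It serves only as a convenient level, not as a placebo background rate, and blur itself is covered by other routes.
- *b*: share of families who believe they are on atropine. All of them report the symptom.
- *r*: share of the remaining families who report it.

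Observed rate = t × [b + (1 − b) × r]. The false gap between arms is t × (b_atropine − b_placebo) × (1 − r).

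Belief equal at 50% (masking intact):
- r = 0.5: 0.13 × (0.5 + 0.5 × 0.5) = 0.0975 in both arms.
- r = 0.7: 0.13 × (0.5 + 0.5 × 0.7) = 0.1105 in both arms.
- The gap is 0, but both rates are below 13%.

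Belief 80% on atropine against 40% on placebo:
- r = 0.5: 0.13 × 0.90 = 0.117 against 0.13 × 0.70 = 0.091, a gap of 2.6 points (ratio 1.29).
- r = 0.7: 0.13 × 0.94 = 0.1222 against 0.13 × 0.82 = 0.1066, a gap of 1.6 points (ratio 1.15).

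For an assumed 30% symptom with the same beliefs, the gap is 0.30 × 0.4 × 0.5 = 6.0 points at r = 0.5 and 0.30 × 0.4 × 0.3 = 3.6 points at r = 0.7.

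If families report whatever they think the cause is (r = 1), the observed rate is 13% in both arms under any pattern of belief.

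**Step 3. Scale.** With 97 randomized, there are about 97 / 3 ≈ 32 children per arm. A gap of 2.6 points is 0.026 × 32 ≈ 0.8 of a child. The standard error of a difference at 13% is √(2 × 0.13 × 0.87 / 32) ≈ 0.084, or about 8 points.

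**The case against.** The strongest defence is that the sentence tells staff what to cover and is not a script. It adds to other checks and does not say that families are asked about nothing else. Subjective complaints can be read as a separate item with no attribution. Symptoms related to the product can mean the known class of atropine symptoms, which is close to the reportable list. Where the plan names someone who judges a link, it is the investigator. Registering change from baseline also implies asking about the same symptoms again. The eCRF pages are not in the documents, so a checklist may exist.

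Much of this stands. A reader might infer that families are asked only for drug-related symptoms and must decide on cause before they speak; the text says neither. A reader might also infer that a full, unfiltered symptom inventory at baseline is compared with a filtered one at follow-up. The baseline item asks about known tendencies, which is a history question and not the same instrument.

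The defence does not remove the mismatch. Both visit-level sentences are worded by attribution, the definition says "not necessarily linked to the treatment", and the other routes leave out itching, dryness and the systemic symptoms. If the sentence can be read in two ways, three sites can also ask in two ways.

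**Conclusion.** The inconsistency in wording is real and worth correcting. It can under-record listed subjective symptoms that have no other route into the data, in a secondary endpoint that also serves two safety hypotheses. With masking intact, the effect is lower rates in all arms, for example 9.8-11.1% observed for a true 13% under the 50% belief assumption.

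It is tempting to conclude that side-effect rates here depend on who believes they are on atropine. The documents do not show that. A false difference between arms needs both attribution-dependent reporting and belief that differs by arm; families are masked, and the plan gives evidence of neither. It is also tempting to quote a gap of about 4-6.5 points (0.13 × 0.3 = 3.9; 0.13 × 0.5 = 6.5). That requires every family to guess its arm correctly. With 80% against 40% belief, the gap is about 1.6-2.6 points, well below the sampling error of a single comparison in a trial of this size. All belief and reporting fractions are assumptions. Pupil size, accommodation, acuity and pressure are unaffected because they do not depend on what families volunteer.

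This is a cheap improvement, not a flaw that undermines the trial.

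**What to change.** Reword the visit question under Registration of adverse events along these lines: *At every remaining visit, before pupil size and accommodation are measured, patients and parents are asked from one fixed checklist about each symptom listed under Reporting adverse effects to the authorities, regardless of suspected cause. Relation to the trial medication is judged afterwards by masked investigators.*

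In the analysis, compare checklist symptom rates between arms and report investigator-judged reactions separately. For visits already completed, state how the question was put at each site and flag those rates as possibly filtered by attribution. If a cause-neutral checklist is already in the eCRF, describing it in the protocol settles the point.

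The cost is one eCRF page and a few minutes per visit, with more minor events recorded in all arms. Enrolment was complete by the end of April 2021, so the change cannot reach baselines already taken. It also alters the question during follow-up, so data from before and after the change should be reported separately. If no visits remain, only the disclosure and the flag apply.

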#### Adverse events and reactions

Adverse event (AE): Any untoward event regarding a participant in the clinical trial treated with an investigational medicinal product, not necessarily linked to the treatment.

Adverse reaction (AR): Any harmful and untoward reaction to an investigational medicinal product with no regards to the dose.

Unexpected adverse reaction (UAR): An adverse reaction of which the character or severity does not match the description of adverse reactions in the summary product characteristics for the given investigational medicinal product.

Serious adverse event (SAE) or serious adverse reaction (SAR): An adverse event or reaction that, regardless of dose, results in death, is life-threatening, causes hospitalization, results in significant or sustained incapacity, or leads to a congenital anomaly or malformation.

Suspected unexpected serious adverse reaction (SUSAR): A suspected unexpected serious adverse reaction which was not expected.

#### Reporting adverse effects to the authorities

As a rule, all adverse events will be registered in a clinical trial on medicinal drugs. However, due to the age, level of activity and healthy nature of the patients involved as well as the duration and logistic possibilities of the study considered, the sponsor-investigator request to waive from this requirement.

Therefore, adverse events and reactions that are considered normal reactions to an eye examination (including stinging when applying eye drops for the examinations and short-term photophobia and blurred vision following eye examination) will not be considered an AE/AR. The sponsor-investigator request that only the following organ-specific symptoms or any likely related symptoms will be reported during the study as AE/AR: visual symptoms (e.g. photophobia, blurred vision and difficulties reading and focusing on text on short distance); eye-related symptoms (e.g. red eye, dry eye, itching eye, stinging or painful eye, changes in lacrimation, allergic reactions such as papillary conjunctivitis, contact dermatitis and lid edema); symptoms of the eye surroundings (e.g. skin changes (i.e. itching, stinging, swelling, redness and dryness); systemic anticholinergic effects (e.g. dryness of skin, mouth and throat from decreased secretion from mucus membranes, flushing, gastrointestinal symptoms, urinary retention and tachycardia). At baseline, patients and parents will be asked to report if the patient has any known tendency within the listed symptoms, e.g. constipation, urinary problems or skin-related problems such as dry or eczematoid skin. For example, if a patient is reported to have a tendency to constipation at baseline, the registration and reporting of AE/AE during study participation will be based upon changes in existing symptoms at baseline.

Due to the requested deviation from the usual procedure regarding registration and reporting of AE/AR, examples of adverse events that are exempted from registration and reporting includes conditions that are common to normal child development and child life (e.g. growth, menarche, common colds, a skin abrasion after falling in the schoolyard, a plantar wart, a superficial cut in the finger after the scout camp, tenderness in the shoulder after travel vaccination. However, if an investigator has the least suspicion that e.g. the superficial cut in the finger is related to difficulties in accommodation the event will be registered and reported as an adverse event.

Sponsor-investigator will report any serious adverse event and reaction (SAE/SAR) as well as suspected unexpected serious adverse reaction (SUSAR) to the Danish Medicines Agency and the Committees on Health Research Ethics for the Capital Region of Denmark. All SAE/SAR will be reported to the sponsorinvestigator by email. All SAE/SAR will be reported to the sponsor-investigator within 24 hours of recognition of the investigator. SAEs will be included in the final report of the study. SARs and SUSARs will be included in an annual report to the Danish Medicines Agency and the Committees on Health Research Ethics for the Capital Region of Denmark. All reports will include a report on the safety of participants and a comment on the consequences for the ongoing trial.

SUSARs that are mortal or life-threatening will be reported by sponsor-investigator as soon as possible and within 7 days from recognition of the sponsor-investigator. All relevant information on follow-up will be reported within 8 days from the initial report. All other SUSARs will be reported within 15 days from recognition.

Since atropine 0.01% and 0.1% eye drops are not yet commercially available, no summary of product characteristics is assessable. As a result, the summary of product characteristics from Minims® (Bausch & Lomb, Chauvin Pharmaceuticals Ltd., UK) Atropine Sulphate 1% will serve as reference document. Due to no available summary of product characteristics for the investigational medicinal product the sponsor-investigator has decided that all SARs will be reported as SUSARs.

When the study has completed all results, adverse events and adverse reactions will be entered in the EudraCT within 1 year. The Danish Medicines Agency will be informed within 90 days from termination of the study.

## Criteria for aborting the study

The entire study will be aborted if one or more of the interventional groups experience a significant worse outcome than the other interventional groups regarding unexpected complications. Interim analyses will be performed when all included patients have completed the first six months, year 1 and year 2.

In case of adverse effect to the trial medication, the participants will be treated according to standard procedures at our research facilities.

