## Study period

The inclusion period began on January 1, 2019 and was completed at the end of April 2021. 124 potential candidates were screened, and 97 research participants were randomized for the intervention. Patients will receive 24 months treatment with atropine or placebo followed by a 12 months washout phase to allow for detection of a possible rebound effect. The last patient visit is scheduled to take place on April 30, 2024. Statistical evaluation of the study results and reporting of findings is scheduled to take approximately 8 months with an expected completion of the study on December 31, 2024. A rough time schedule is presented in Table 1. The authorities will be informed when the study has finished. If finished at the

	2018				2019				2020					20	21		2022				2023				2024			
Quarter	1	2	3	4	1	2	3	4	1	2	3	4	1	2	3	4	1	2	3	4	1	2	3	4	1	2	3	4
Application for Danish Medicines Agency	•	•																										
Application for National Committee on Health Research Ethics			•	•																								
Application for Data Protection Agency			•	•																								
Recruitment and follow-up					•	•	•	•	•	•	•	•	•	•	•	•	•	•	•	•	•	•	•	•	•	•		
Ph.D. courses					•	•	•	•	•	•	•	•	•	•	•	•			•	•	•	•	•	•	•	•		
Papers and theses																•	•	•	•	•	•	•	•	•	•	•	•	•

planned date authorities will be informed within 90 days, if finished earlier authorities will be informed within 15 days.

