#### Blinding

Allocation concealment is performed by masking the investigators, additional study team performing the ocular measurements, parents and patients to randomization status throughout the entire study period. All statistical analyses will be performed masked to randomization status. A list linking participant study identification number to randomization status will be kept under lock in a designated space unavailable to study investigators. Trial medication will be prepackaged from external collaborator #1 so that bottles are pre-labeled according to the European rules on labelling of trial medicines (see *Appendix 1*) and of similar appearance.

If necessary, sponsor-investigator will be unblinded as to participants treatment status as described above. All statistical analyses will be performed in a masked fashion allowing sponsor-investigator to part of the analyses.

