## Sample size and data analysis

The primary endpoint of the present study is the mean change in axial length 36 months after baseline. Axial length is strongly related to the refraction of the eye and since we do not have valid data for axial length elongation in Danish myopic children, the power calculations have been performed using the refraction (in spherical equivalent) as a surrogate measure. A progression in untreated childhood myopia of  $-1.2 \pm 0.69$  diopters yearly has been shown in Asian children (ATOM1 study). (33) A similar myopia progression rate has been documented in untreated Danish school children. (42) Given a significance level (alpha) of 0.05 and a statistical power (type 2 error) of 80%, a study size of 21 patients in each interventional arm will be needed, assuming a difference in myopia progression of 50% after 36 months. In order to compensate for the study length and drop-out rates and unknown effect of low-dose atropine in non-Asian children, 50 patients will be included in each interventional arm.

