## Risks, side effects and inconveniences

The use of atropine 1% eye drops has been approved for cycloplegia, mydriasis and penalization of the healthy eye in the treatment of amblyopia. The most frequently reported side effects of atropine 1% eye drops include photophobia, blurred vision, decreased lacrimation and allergic reactions such as papillary conjunctivitis, contact dermatitis and lid edema. Systemic side effects rarely occur but include anticholinergic effects such as dryness of skin, mouth and throat from decreased secretion from mucus membranes, flushing, gastrointestinal symptoms, urinary retention and tachycardia. Systemic absorption may be reduced by gently compressing the lacrimal sac at the medial canthus for a minute during and following the instillation of the drops. This blocks the passage of the drops via the naso-lacrimal duct to the wide absorptive area of the nasal and pharyngeal mucosa.

The use of low-dose atropine has not yet been approved for the treatment of myopia and is not yet commercially available. In the ATOM 2 study, the reported side effects of atropine 0.01% and 0.1% were low. The pupil size under both photopic and mesopic conditions increased only 1 and 3 millimeters,

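### Three interim analyses fall within masked follow-up, and the plan lets an examining sponsor-investigator join them with only arm coding as protection

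*Combined protocol and SAP*

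**What the plan says.** - *Criteria for aborting the study*: "Interim analyses will be performed when all included patients have completed the first six months, year 1 and year 2". The preceding sentence gives the only decision rule in that section: the whole study is aborted if one or more arms "experience a significant worse outcome than the other interventional groups regarding unexpected complications". The section names no interim endpoint, test, threshold, analyst or recipient.
- *Blinding*: masking covers investigators, measuring staff, "parents and patients to randomization status throughout the entire study period". All analyses are to be masked to allocation, and the section expressly allows the sponsor-investigator to take part in them.
- *Randomization*: after an emergency code break, the sponsor-investigator stops examining participants. This implies that the sponsor-investigator examines them otherwise.
- *Risks, side effects and inconveniences*, citing the earlier low-dose atropine trial: "The pupil size under both photopic and mesopic conditions increased only 1 and 3 millimeters" with 0.01% and 0.1% respectively. Accommodation amplitude fell to 11.3 D with 0.01% and 3.8 D with 0.1%.
- *Endpoints*: both primary endpoints, axial length and spherical equivalent, are set at 36 months.
- *Study period*: inclusion ended at the end of April 2021 with 97 children randomized, and the last visit is on 30 April 2024. Evaluation and reporting are given about 8 months, to finish on 31 December 2024. In the time schedule, the row "Papers and theses" starts in the fourth quarter of 2021.

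**The concern.** An abort rule that compares arms needs arm-separated data, so each interim creates such data while children are still being treated or followed in washout. The plan does not separate the people who see these data from the people who examine the children. The one person it names as joining the analyses appears to be an examiner too.

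The safeguard is coding. Coding works poorly when a drug leaves a visible signature, and pupil size and accommodation are measured at every standard visit.

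An examiner who learned allocations or saw the efficacy trend could, without intending to, affect what follows:

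- Unsuitable auto-refraction readings are discarded partly on judgement.
- The investigator decides whether bifocal or photochromatic spectacles are indicated.
- Encouragement to keep using the drops or to stay in the study may differ between children.

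Axial length is read by an instrument under a repeatability criterion and leaves less room for this. Spherical equivalent, the other primary endpoint, leaves more. The rebound hypothesis rests wholly on the washout year, which comes late in this exposure.

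**Working it through.** **1. Timing.** Inclusion closed at the end of April 2021. Adding 6, 12 and 24 months puts the interims at about the end of October 2021, April 2022 and April 2023. These dates are 30, 24 and 12 months before the last visit. At the first interim no child has reached month 36, because a child included on 1 January 2019 gets there in January 2022. Every child enrolled after October 2019 is still within the 24-month treatment phase.

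**2. Can coded arms be recognised?** There are 97/3, or about 32, children per arm. The standard error of a difference between two arm means is SD × √(2/32) = 0.25 × SD. The documents give no SD for pupil size, so the result is stated as a threshold:

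- 0.1% against 0.01%: 3 − 1 = 2 mm, or 2/(0.25 × SD) = 8/SD standard errors. This exceeds two standard errors for any SD below 4 mm.
- 0.01% against placebo: 1 mm if placebo pupils do not change (an assumption), or 4/SD standard errors. This exceeds two for any SD below 2 mm.
- One child's reading: the same 1 mm is only 1/SD standard deviations, a quarter of the separation seen between group means.

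Arm means can therefore reveal the codes, including 0.01% against placebo, where a single reading might not. Accommodation (11.3 D against 3.8 D) points the same way for the loading arm. The first interim comes after the 0.1% phase has ended, but its data include months 3 and 6, when that dose was in use. A summary table by code reveals which code is which. A dataset listing codes by child then reveals each child's allocation.

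**3. Error rate.** The plan's sample size reproduces as a single test: n = 2 × [0.69 × (1.960 + 0.842)/0.6]² = 20.76, rounded up to 21 per arm, using the yearly SD of 0.69 D and half of 1.2 D. It contains no allowance for several looks.

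Suppose one contrast on one endpoint were tested at two-sided 0.05 at months 6, 12, 24 and 36. The chance of at least one false positive, from simulated correlated z-statistics, depends on how the looks correlate:

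| Correlation between looks | False-positive risk |
|---|---|
| Independent increments, √(s/t) | 13.6% |
| Constant 0.9 | 9.3% |
| Independent looks, upper reference, 1 − 0.95⁴ | 18.5% |
| Interims cannot lead to an efficacy claim | 5% |

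Both the two-sided level and efficacy testing at the interims are assumptions. The plan states neither.

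**The case against.** The strongest reply is that the plan already makes every analysis masked, ties the interims to safety alone, and fixes the primary endpoints at month 36. Much of this stands, and it rules out three stronger readings that a reader might infer.

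- *That early papers will publish arm-level results.* The papers row does start in the quarter of the first interim, but the documents never state the papers' content. It could be baseline or pooled work, such as the choroidal-thickness predictor hypothesis. *Study period* places evaluation and reporting in about 8 months ending in December 2024.
- *That masking fails.* The cited pupil and accommodation figures are group values from another trial, given without SDs. They do not show that individual children can be classified. A summary table alone would not identify a child.
- *That efficacy can be claimed at any of four looks.* The section contains no efficacy rule. The 9% to 14% is hypothetical.

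It is also fair to say that examiners see each child's pupils at every visit, so some guessing would occur without any interim. What an interim adds is confirmation of the codes, the contrast between 0.01% and placebo, and the efficacy trend. Masked analysis does not remove this when the person receiving the coded data also examines the children.

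**Conclusion.** The concern holds as a gap in protection. The plan schedules three between-arm analyses during masked follow-up and admits an apparent examiner to all statistical analyses. It relies on coding that group pupil and accommodation data could undo. This goes beyond missing detail, because following the arrangement as written can give an examiner arm-separated data 30, 24 and 12 months before the last visit.

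The conclusion assumes that the sponsor-investigator does examine children, as *Randomization* implies. It also assumes that group differences here resemble those quoted from the earlier trial. Learning individual allocations further requires access to a dataset listing codes by child.

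The documents give no basis for sizing the resulting bias. The inflated false-positive risk applies only if efficacy is tested at the interims. If they are confined to safety, the final efficacy level for a single contrast is unaffected. The change is worth making because it is cheap and removes an avoidable route to bias in the month-36 results.

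**What to change.** - *Criteria for aborting the study*: state that the three interims address only the safety rule already given, are run by someone who examines no children, and return only continue or stop.
- *Blinding*: let the sponsor-investigator and other examiners join arm-separated analyses, coded or not, only after the last month-36 visit.
- *Sample size and data analysis*: state that any between-arm efficacy result produced before then is secondary and that the efficacy conclusion is drawn only at month 36. A full embargo on earlier arm-level papers is not required. It would be a trade-off for the sponsor, since a published group result discloses the trend but not any child's allocation.
- This version records inclusion as complete, so an interim may already have been run. If so, record who saw which data.

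**Cost.** The change is mainly wording. The sponsor-investigator loses early access to arm-separated data. The budget lists statistical assistance of 25,000 DKK in 2021, 50,000 in 2022, none in 2023 and 50,000 in 2024, so the year-2 interim (about April 2023) needs some of that time moved. Moving is more realistic than adding, because listed expenses exceed grants by 7,828,500 − 7,453,500 = 375,000 DKK.
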